10.3 Use of Specimens in Research

Digitally scanned H&E slides will be distributed to NeoGenomics Laboratories for PD-L1 Immunohistochemistry. See Section [11](#) for the description of the laboratory research studies to be performed.

Specimens from patients who consented to allow their specimens to be used for future undefined research studies will be retained in an ECOG-ACRIN designated central repository.

NOTE: Specimens will not be used for future research studies that are not defined in this protocol until an amendment to this treatment protocol or a separate correlative science protocol is reviewed and approved in accordance with National Clinical Trials Network (NCTN) policies.

For this trial, specimens will be retained at the ECOG-ACRIN Central Biorepository and Pathology Facility.

Specimens submitted will be processed to maximize their utility for current and future research projects. Tissue processing may include, but not limited to, extraction of DNA and RNA and construction of tissue microarrays (TMAs).

Any residual blocks will be available for purposes of individual patient management on specific written request.

If future use is denied or withdrawn by the patient, the specimens will be removed from consideration for use in any future research study. Pathology materials may be retained for documentation purposes or returned to the institution. All other specimens will be destroyed per guidelines of the respective repository.

10.4 Sample Inventory Submission Guidelines

Inventories of all specimens submitted from institutions will be tracked via the ECOG-ACRIN STS and receipt and usability verified by the receiving laboratory. Inventories of specimens forwarded and utilized for approved laboratory research studies will be submitted by the investigating laboratories to the ECOG-ACRIN Operations Office - Boston on a monthly basis in an electronic format defined by the ECOG-ACRIN Operations Office - Boston.

11. Laboratory Research Studies

11.1 Reference PD-L1 Testing and Correlation with Outcome.

Reason for study: We propose to do PD-L1 testing on tumor tissue obtained for this study. In the CheckMate 057 nivolumab trial, improvements in overall survival and progression-free survival were predicted by PD-L1 expression on tumors. [8] However, some patients that responded did not have tumor PD-L1 expression. This biomarker was approved as a complementary diagnostic test to help predict the probability of response in patients who receive this therapy. It may not be done routinely under standard of care on patients enrolled in this study.

Since patients on both arms will be receiving nivolumab, we are integrating this test primarily to identify potential imbalances with regard to PD-L1 status. We are not proposing real-time testing because this would likely result in delays of treatment. Thus, we will batch test retrospectively and use this test to adjust the outcome results for the impact of PD-L1 expression status in multivariable models. We expect PD-L1 positive patients to have a PFS approximately double that of PD-L1 negative patients (PFS HR = 0.5) and will use this to adjust our outcome models.

Test details:

Test: PD-L1 IHC 28-8 pharmDx test

Formalin-fixed paraffin embedded tumor tissue (blocks or slides) will be collected at baseline. Archival specimens from prior biopsies are allowed. Cytologic specimens are allowed as long as they contain sufficient material for routine immunohistochemical testing.

This study is FDA approved and used for clinical care. Results from this testing will be used to retrospectively determine PD-L1 positivity in tumor specimens from this trial to evaluate its association with progression-free and overall survival, as well as RECIST response.

Specimens will be batched and analyzed at one central laboratory. This will be performed by the CLIA certified laboratory, NeoGenomics. This test will be performed by standard immunohistochemical methods as per the FDA approved criteria. More information is available here:

http://www.neogenomics.com/t_test/pd-l1/

Results will be reported as a percentage of tumor positivity ranging from 0-100%. Categories will be determined at the time of analysis, which may include any of the following or other cutpoints not listed below:

- < 1% (zero) expression
- ≥ 1% expression
- ≥ 5% expression
- ≥ 10% expression

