2.3 Correlative Endpoints

- 2.3.1 To adjust progression free survival for each arm based on PD-L1 tumor status

Rev. Add2

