9.3 Statistical Analysis Plan

The primary and some secondary analyses will include all eligible and treated patients. Exceptions to this include: analysis of toxicity data, which will include all patients who received study drug regardless of eligibility, and analyses of response, which will include eligible and treated patients with measurable and evaluable disease.

Time-to-event data, such as PFS and OS, will be estimated using the Kaplan-Meier method, and Cox proportional hazards models will be used to estimate the treatment hazard ratios. The primary comparison of PFS will use a logrank test stratified on the randomization stratification factors with a one-sided type I error rate of 10%. Other comparisons of groups will be made using the logrank test and Cox modeling.

Categorical data, such as response rates (CR+PR) and toxicity, will be compared using Fisher's exact tests with a one-sided type I error rate of 10%; multivariable logistic regression modeling will be used to adjust for the effect of any covariates that are associated with these categorical outcomes. Though none are currently planned, any continuous outcomes will be analyzed using Wilcoxon rank sum test, and multivariable linear regression models may be used to adjust for multiple associations with outcome.

Modeling procedures will implement backward selection; variables significant at the 0.10 level in the univariate setting will be chosen for inclusion in an initial full model, and at each step the least significant variable will be removed from the model. Only those covariates with $p < 0.05$ will remain in any final models, unless there are factors identified by the study team as crucial to model interpretation.

Point estimates of all endpoints will be accompanied by the corresponding two-sided 80% confidence intervals.

In the event that there are missing data, no imputation of the missing data will be conducted. We will assume that data are missing at random and will conduct all analyses as originally planned because we do not anticipate an excess of missing data.

Subset analyses are planned for all stratification factors and all known prognostic factors, such as performance status, age, sites of metastases, gender, etc. Subset analyses of all variables, including correlatives, are considered to be exploratory in nature.

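### Does leaving the central PD-L1 cutpoint open until analysis undermine the PD-L1-adjusted PFS models?

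*Combined protocol and SAP*

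**What the plan says.** Objective 2.3.1, listed under correlative endpoints, is "To adjust progression free survival for each arm based on PD-L1 tumor status". Section 11.1 has archival or baseline tissue tested centrally in retrospective batches with the 28-8 assay. It gives the result three uses: first and mainly, to look for imbalance between arms; second, to "use this test to adjust the outcome results for the impact of PD-L1 expression status in multivariable models"; third, to "evaluate its association with progression-free and overall survival, as well as RECIST response".

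On scale and coding, Section 11.1 says "Results will be reported as a percentage of tumor positivity ranging from 0-100" per cent, and then "Categories will be determined at the time of analysis, which may include any of the following or other cutpoints not listed below". The list that follows is below 1%, at least 1%, at least 5% and at least 10%. On effect size it says "We expect PD-L1 positive patients to have a PFS approximately double that of PD-L1 negative patients", with a PFS hazard ratio of 0.5, and does not define positive.

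Section 9.3 sets the general modelling rule: "variables significant at the 0.10 level in the univariate setting will be chosen for inclusion in an initial full model". After backward elimination, covariates with p below 0.05 "will remain in any final models, unless there are factors identified by the study team as crucial to model interpretation". The same section bases the primary PFS comparison on a logrank test stratified by the randomization factor, and calls subset analyses of all variables, correlatives included, exploratory.

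The 1% cut in Sections 4.2.5 and 9.7 belongs to a different variable: local PD-L1 status from any validated platform, with a third level for unknown or not tested.

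**The concern.** Three features together look like an uncontrolled analysis choice. The list of cutpoints is open-ended. The categories are set when outcomes may already be known. And Section 9.3 selects covariates by p-value, so the cut could decide whether PD-L1 enters the adjusted model at all.

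If so, the adjustment that objective 2.3.1 calls for could appear or vanish with the cut, a PD-L1 association could be reported at whichever cut looks strongest, and the adjusted treatment hazard ratio could move with the coding.

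**Working it through.** **1. Does the primary analysis depend on the central result?** Inputs from Sections 9.4 and 9.5: 74 events per comparison, hazards 0.173 and 0.096, one-sided 0.10, 43 patients per arm, about 15 months of accrual and 9-10 months of follow-up.

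- Hazard ratio = 0.096/0.173 = 0.555, and |ln HR| = 0.589.
- Power = Φ(√74/2 × 0.589 − 1.282) = Φ(2.533 − 1.282) = Φ(1.252) = 0.895. The plan states 89%.
- Randomized number = 129/0.90 = 143.3, so 144, as stated.
- Expected events in two arms of 43, with exponential PFS and uniform accrual: 73.2-74.6. The plan states 74.

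The design reproduces, and no input is a central PD-L1 value.

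**2. What if the best of the three listed cuts were picked?** The documents give no PD-L1 distribution, so the shares below 1 / 1-5 / 5-10 / at least 10% are assumed.

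- First set (6,000 runs each): 45/15/8/32, 30/20/15/35, 50/10/5/35, 60/10/5/25.
- Second set (1,500-2,500 runs): 45/10/10/35, 25/25/25/25, 60/8/7/25.
- All patients are assumed to have a central result. PFS is exponential, and the analysis is at 25 months.

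Results over both sets. The association test uses 129 patients and no PD-L1 effect. The treatment test uses 86 patients, no treatment effect and, in the main case, a PD-L1 hazard ratio of 0.5 at 1%; the second set also tried a graded effect.

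| Test | Fixed 1% cut | Cut chosen by fit to PFS | Cut chosen for best result on that test |
|---|---|---|---|
| PD-L1 association, two-sided 5% | 5-6% | – | 10-13% |
| PD-L1 association, one-sided 10% | 9-11% | – | 16-21% |
| Adjusted treatment effect, one-sided 10% | 9-11% | 10-11% (first set only) | 12-14% |

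Three independent tests would give 1 − 0.95³ = 14.3% and 1 − 0.90³ = 27.1%. The simulated rates are lower because the cuts are nested and their tests correlated. The treatment test hardly moves when the cut is chosen by fit, because randomization makes treatment independent of PD-L1 and that choice does not look at the treatment effect. Adjusted treatment hazard ratios across the three cuts differ by a median factor of 1.05-1.07 (90th percentile 1.13-1.19). With a true PD-L1 hazard ratio of 0.5 at 1%, the estimate is 0.49-0.50 at the 1% cut and 0.49 at the best-fitting cut.

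**3. Does the Section 9.3 selection rule make the adjustment depend on the cut?** Applying the rule mechanically (univariate p below 0.10, then p below 0.05 with treatment in the model), with 129 patients and a hazard ratio of 0.5 at a true threshold of 1%, PD-L1 is retained in 94-96% of trials at the 1% cut, 51-81% at 5% and 27-70% at 10%. The cuts disagree on retention in 29-72% of trials, or 17-53% if the true threshold is 5% or 10%.

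These figures mostly measure the cost of using a wrong cut, not of leaving the cut open. A 10% cut named in advance would lose exactly the same power. Trials that retain PD-L1 under at least one cut include all those that retain it at 1%, so an open choice made by fit cannot retain it less often than the fixed 1% cut. The true threshold of 1% is also an assumption, since Section 11.1 leaves positive undefined.

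Read together, the sections do not point to mechanical selection. Section 11.1 states the adjustment without condition, objective 2.3.1 makes it the purpose, and Section 9.3 exempts factors the team considers crucial. PD-L1 is the obvious candidate for that exemption.

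**4. The imbalance check.** Section 11.1 names no scale for it. With 43 patients per arm, the chance of a difference above 15 points between two arms is 11-15% at the 1% cut and 23-28% at any of three cuts. The check is therefore free of the coding question only if made on the 0-100% values or shown at every cut. It uses no outcome data in either case.

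**The case for a change.** The best argument for a change is that PD-L1-adjusted PFS is a stated objective, so the plan should say what the covariate is. Nothing requires the coding to be settled before central results meet outcome data, and two or three sentences would settle it. The exploratory label in Section 9.3 is attached to subset analyses and does not tell the analyst which covariate to fit.

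Part of this stands. The coding is not written down, the 1% stratification cut does not supply it, and a PD-L1 association reported at a selected cut would carry about double its nominal error.

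The rest does not carry. That doubling needs selection after outcomes are seen, followed by reporting of one cut alone. Section 11.1 speaks of categories in the plural and allows any of those listed, which fits a display of all of them. Deferral also has an ordinary reason: tissue is batch-tested retrospectively, and how many patients fall in each band is unknown until then. Section 9.3 gives no significance level for a PD-L1 association with PFS or OS; the one-sided 10% level is set for the primary comparison and the Fisher tests, and 0.05 is a retention rule. No declared error rate for those PFS and OS associations is therefore breached. Naming a cut now would not protect the adjustment either, because the loss in step 3 follows from naming the wrong one.

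**Conclusion.** No change is needed. The observation is accurate: the coding of the central PD-L1 result is open, and no other section closes it. But it is a missing definition in a correlative analysis. Followed as written, the plan gives no wrong result. A statistician will normally settle a main form of the covariate and show the other cuts beside it.

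The effect on the primary test is nil, and error in the adjusted treatment test stays at 10-11% whether the cut is fixed or chosen by fit. It reaches 12-14% only if the cut is picked for the most favourable treatment result, which nothing in the plan suggests. The one material exposure is a PD-L1/PFS association at a selected cut, about 5% rising to 10-13% for an assumed two-sided 5% test. A reader of the results can guard against it by asking whether all listed cuts are shown, and the imbalance check deserves the same reading.

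These sizes rest on assumed PD-L1 distributions, exponential PFS and complete central results, and other Section 9.3 covariates were not modelled. The conclusion for the primary test needs none of those assumptions.

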11.2 Lab Data Transfer Guidelines

The data collected on the above mentioned laboratory research studies will be submitted electronically using a secured data transfer to the ECOG-ACRIN Operations Office - Boston by the investigating laboratories on a quarterly basis or per joint agreement between ECOG-ACRIN and the investigator. The quarterly cut-off dates are March 31, June 30, September 30, and December 31. Data is due at the ECOG-ACRIN Operations Office - Boston 1 week after these cut-off dates.

12. Electronic Data Capture

Please refer to the **EA5152** Forms Completion Guidelines for the forms submission schedule. Data collection will be performed in Medidata Rave and EASEE-PRO (for tobacco use assessment).

This study will be monitored by the Clinical Data Update System (CDUS) version 3.0. Cumulative protocol and patient-specific CDUS data will be submitted electronically to CTEP on a quarterly basis by FTP bust of data. Reports are due January 31, April 30, July 31, and October 31. Instructions for submitting data using the CDUS can be found on the CTEP web site (<http://ctep.cancer.gov/reporting/cdus.html>).

13. Patient Consent and Peer Judgment

Current FDA, NCI, state, federal and institutional regulations concerning informed consent will be followed.

14. References

1. Siegel, R., D. Naishadham, and A. Jemal, *Cancer statistics*, 2012. CA Cancer J Clin, 2012. **62**(1): p. 10-29.
2. Jemal, A., et al., *Global cancer statistics*. CA Cancer J Clin, 2011. **61**(2): p. 69-90.
3. Schiller, J.H., et al., *Comparison of four chemotherapy regimens for advanced non-small-cell lung cancer*. N Engl J Med, 2002. **346**(2): p. 92-8.
4. Hanna, N., et al., *Randomized phase III trial of pemetrexed versus docetaxel in patients with non-small-cell lung cancer previously treated with chemotherapy*. J Clin Oncol, 2004. **22**(9): p. 1589-97.
5. Hellerstedt, B.A., et al., *Activity of cabozantinib (XL184) in metastatic NSCLC: Results from a phase II randomized discontinuation trial (RDT)*. J Clin Oncol, 2012. **30**(suppl): p. Abstr 7514.
6. Neal, J.W., et al., *Cabozantinib (C), erlotinib (E) or the combination (E+C) as second- or third-line therapy in patients with EGFR wild-type (wt) non-small cell lung cancer (NSCLC): A randomized phase 2 trial of the ECOG-ACRIN Cancer Research Group (E1512)*. J Clin Oncol, 2015. **33**(Suppl): p. Abstr 8003.

Appendix I

Pathology Submission Guidelines

The following items are included in Appendix I:

1. Guidelines for Submission of Pathology Materials
(instructional sheet for Clinical Research Associates [CRAs])
2. Instructional memo to submitting pathologists
3. ECOG-ACRIN Generic Specimen Submission Form (#2981)

Guidelines for Submission of Pathology Materials

The following pathology materials are to be submitted within one (1) month of randomization:

1. Pathology Submissions:

- Formalin-fixed paraffin-embedded (FFPE) tumor tissue block

NOTE: If blocks are unavailable for submission, cores and slides are to be submitted. All cores and slides must be adequately labeled, with slides numbered sequentially in the order cut. Alternative submission requirements:

- One (1) H&E slide
- Twenty (20) 5 µm unstained, uncharged air-dried plus slides from the thickest part of the tumor
- One (1) or more core punches (minimum of 4mm diameter). If core punch tool is unavailable, request core punch kit from the ECOG-ACRIN CBPF [contact]

If these criteria cannot be met, please contact the ECOG-ACRIN CBPF ([contact]) to obtain alternative submission requirements.

2. Forms and Reports:

NOTE: Adequate patient identifying information must be included with every submission. It is strongly recommended that full patient names be provided. The information will be used only to identify patient materials, and will help to expedite any required communications with the institution (including pathologists).

The following items are to be included with the pathology materials:

- Institutional Pathology Report
- ECOG-ACRIN Generic Specimen Submission Form (#2981) [if STS is unavailable]
- Sample Tracking System (STS) Shipping Manifest Form
- Immunological study reports, if available

3. Mail pathology materials to:

ECOG-ACRIN Central Biorepository and Pathology Facility
MD Anderson Cancer Center
Department of Pathology, Unit 085
Tissue Qualification Laboratory for ECOG-ACRIN, Room G1.3586
[name]
[name]
Phone: Toll Free [contact] [contact] Local or International Sites)
[contact]
Email: [contact]

If you have any questions concerning the above instructions or if you anticipate any problems in meeting the pathology material submission deadline of one month, contact the Pathology Coordinator at the ECOG-ACRIN Central Biorepository and Pathology Facility by [contact] or email: [contact]

Reshaping the future of patient care

[name], and [name], PhD
Group Co-Chairs

MEMORANDUM

TO:

(Submitting Pathologist)

FROM:

[name]., Chair
ECOG-ACRIN Laboratory Science and Pathology Committee

DATE:

SUBJECT: Submission of Pathology Materials for EA5152: A Randomized Phase II Trial of Nivolumab, Cabozantinib Plus Nivolumab, and Cabozantinib Plus Nivolumab Plus Ipilimumab in Patients with Previously Treated Non-Squamous NSCLC

The patient named on the attached request has been entered onto an ECOG-ACRIN protocol by _____ (ECOG-ACRIN Investigator). This protocol requires the submission of pathology materials for defined laboratory research studies.

Keep a copy of the submission for your records and return any relevant completed forms, the surgical pathology report(s), the slides and/or blocks and any other required material to the Clinical Research Associate (CRA). The CRA will forward all required pathology materials to the ECOG-ACRIN Central Biorepository and Pathology Facility (CBPF).

Pathology materials submitted for this study will be retained at the ECOG-ACRIN Central Repository for future research studies per patient consent. Paraffin blocks will be returned upon written request for purposes of patient management.

Please note: Since blocks are being used for laboratory research studies, in some cases the material may be depleted, and, therefore, the block may not be returned.

If you have any questions regarding this request, please contact the ECOG-ACRIN Central Biorepository and Pathology Facility at ([name] [contact] Local or International Sites) or email: [contact]

The ECOG-ACRIN CRA at your institution is:

Name: _____

Address: _____

Phone: _____

Thank you.

ECOG-ACRIN Generic Specimen Submission Form

Form No. 2981v3

Page 1 of 1

Institution Instructions: This form is to be completed and submitted with **all specimens** ONLY if the Sample Tracking System (STS) is not available. **Use one form per patient, per time- point.** All specimens shipped to the laboratory must be listed on this form. Enter all dates as MM/DD/YY. Keep a copy for your files. Retroactively log all specimens into STS once the system is available. **Contact the receiving lab to inform them of shipments that will be sent with this form.**

Protocol Number _____ Patient ID _____ Patient Initials Last _____ First _____

Date Shipped _____ Courier _____ Courier Tracking Number _____

Shipped To (Laboratory Name) _____ Date CRA will log into STS _____

FORMS AND REPORTS: Include all forms and reports as directed per protocol, e.g., pathology, cytogenetics, flow cytometry, patient consult, etc.

Required fields for all samples		Additional fields for tissue submissions					Completed by Receiving Lab
Protocol Specified Timepoint:							
Sample Type (fluid or fresh tissue, include collection tube type)	Quantity	Collection Date and Time 24 HR	Surgical or Sample ID	Anatomic Site	Disease Status (e.g., primary, mets, normal)	Stain or Fixative	Lab ID

Fields to be completed if requested per protocol. Refer to the protocol-specific sample submissions for additional fields that may be required.

Leukemia/Myeloma Studies:	Diagnosis	Intended Treatment Trial	Peripheral WBC Count (x1000)	Peripheral Blasts %	Lymphocytes %
Study Drug Information:	Therapy Drug Name	Date Drug Administered	Start Time 24 HR	Stop Time 24HR	
Caloric Intake:	Date of Last Caloric Intake		Time of Last Caloric Intake 24HR		

CRA Name _____ CRA Phone _____ CRA Email _____

Comments

9/12/14

A Randomized Phase II Trial of Nivolumab, Cabozantinib Plus Nivolumab, and Cabozantinib Plus Nivolumab Plus Ipilimumab in Patients with Previously Treated Non-Squamous NSCLC

